5.5.1 Response Criteria

5.5.1.1 Evaluation of Target Lesions

Complete Response (CR): Disappearance of all target lesions. Any pathological lymph nodes (whether target or non-target) must have reduction in short axis to <10 mm.

Partial Response (PR): At least a 30% decrease in the sum of the diameters of target lesions, taking as reference the baseline sum diameters.

Progressive Disease (PD): At least a 20% increase in the sum of the diameters of target lesions, taking as reference the smallest sum on study (this includes the baseline sum if that is the smallest on study). In addition to the relative increase of 20%, the sum must also demonstrate an absolute increase of at least 5 mm. (Note: the appearance of one or more new lesions is also considered progressions).

Stable Disease (SD): Neither sufficient shrinkage to qualify for PR nor sufficient increase to qualify for PD, taking as reference the smallest sum diameters while on study.

5.5.1.2 Evaluation of Non-Target Lesions

Complete Response (CR): Disappearance of all non-target lesions and normalization of tumor marker level. All lymph nodes must be non-pathological in size (<10 mm short axis).

Note: If tumor markers are initially above the upper normal limit, they must normalize for a patient to be considered in complete clinical response.

Non-CR/Non-PD: Persistence of one or more non-target lesion(s) and/or maintenance of tumor marker level above the normal limits.

Progressive Disease (PD): Appearance of one or more new lesions and/or *unequivocal progression* of existing non-target lesions. *Unequivocal progression* should not normally trump target lesion status. It must be representative of overall disease status change, not a single lesion increase.

Although a clear progression of “non-target” lesions only is exceptional, the opinion of the treating physician should prevail in such circumstances, and the progression status should be confirmed later by the review panel (or Sponsor).

5.5.1.3 Evaluation of New Lesions

The finding of a new lesion should be unequivocal (i.e. not due to difference in scanning technique, imaging modality, or findings thought to represent something other than tumor (for example, some ‘new’ bone lesions may be simply healing or flare of pre-existing lesions). However, a lesion identified on a follow-up scan in an anatomical location that was not scanned at baseline is considered new and will indicate PD. If a new lesion is equivocal (because of small size etc.), follow-up evaluation will clarify if it truly represents new disease and if PD is confirmed, progression should be declared using the date of the initial scan on which the lesion was discovered.

5.5.1.4 Evaluation of Best Overall Response

The best overall response is the best response recorded from the start of the treatment until disease progression/recurrence (taking as reference for progressive disease the smallest measurements recorded since the treatment started). The patient's best response assignment will depend on the achievement of both measurement and confirmation criteria.

Table 5-2: Participants with Measurable Disease (Target Disease)

Target Lesions	Non-Target Lesions	New Lesions	Overall Response	Best Overall Response when Confirmation is Required*
CR	CR	No	CR	>4 wks Confirmation**
CR	Non-CR/Non-PD	No	PR	≥4 wks Confirmation**
CR	Not evaluated	No	PR	
PR	Non-CR/Non-PD/not evaluated	No	PR	
SD	Non-CR/Non-PD/not evaluated	No	SD	Documented at least once ≥4 wks from baseline**
PD	Any	Yes or No	PD	no prior SD, PR or CR
Any	PD***	Yes or No	PD	
Any	Any	Yes	PD	
* See RECIST 1.1 manuscript for further details on what is evidence of a new lesion.				
** Only for non-randomized trials with response as primary endpoint.				

*** In exceptional circumstances, unequivocal progression in non-target lesions may be accepted as disease progression.

Note: Participants with a global deterioration of health status requiring discontinuation of treatment without objective evidence of disease progression at that time should be reported as “*symptomatic deterioration.*” Every effort should be made to document the objective progression even after discontinuation of treatment.

Table 5-3: Participants with Non-Measurable Disease (Non-Target Disease)

Non-Target Lesions	New Lesions	Overall Response
CR	No	CR
Non-CR/non-PD	No	Non-CR/non-PD*
Not all evaluated	No	not evaluated
Unequivocal PD	Yes or No	PD
Any	Yes	PD
* ‘Non-CR/non-PD’ is preferred over ‘stable disease’ for non-target disease since SD is increasingly used as an endpoint for assessment of efficacy in some trials so to assign this category when no lesions can be measured is not advised		

6 SAFETY

6.1 Adverse Events and Laboratory Abnormalities

6.1.1 Adverse Events

An AE is any untoward medical occurrence in a patient or clinical trial subject administered a medicinal product and which does not necessarily have a causal relationship with this treatment. An adverse event can therefore be any unfavorable and unintended sign (e.g. an abnormal laboratory finding), symptom, or disease temporarily associated with the use of a medicinal product, whether or not considered related to the medicinal product. An adverse event can arise from any use of the drug (e.g. off-label use, use in combination with another drug) and with any route of administration, formulation, or dose, including an overdose. This definition also includes AEs associated with medication errors and uses of the investigational product outside what is in the protocol, including misuse and abuse. Pre-existing medical conditions that worsen during the study should be recorded as AEs. Abnormal laboratory values, ECG findings, or vital signs are to be recorded as AEs if they meet the criteria described in this protocol. All untoward events that occur from time of first study drug dose through 30 days after the decision to discontinue study treatment (or the date the subject is deemed to be a screen failure) are to be recorded by the investigational site. This requirement includes AEs from unscheduled as well as scheduled visits and includes the new onset of or increase in pain during this period.

6.1.2 Serious Adverse Events

The SAE definition and reporting requirements are in accordance with the International Conference of Harmonisation (ICH) Guideline for Clinical Safety Data Management: Definitions and Standards for Expedited Reporting, Topic E2A.

An SAE is defined as any untoward medical occurrence that at any dose:

- Result in death;
- Is life-threatening (i.e., in the opinion of the investigator, the AE places the subject at risk of death; it does not include an event that, had it occurred in a more severe form, might have caused death);
- Requires inpatient hospitalization or results in prolongation of an existing hospitalization;
 - Note: While most hospitalizations necessitate reporting of an SAE, some hospitalizations do not require SAE reporting, as follows: elective or previously scheduled surgeries or procedures for pre-existing conditions that have not worsened after initiation of treatment (e.g., a previously scheduled ventral hernia repair); pre-specified study hospitalizations for observation; or events that result in hospital stays of fewer than 24 hours and that do not require admission (e.g., an ER visit for hematuria that results in a diagnosis of cystitis and discharge home on oral antibiotics). SAEs must, however, be reported for any surgical complication resulting in prolongation of the hospitalization.
- Results in persistent or significant disability or incapacity:
 - Note: The term “disability” refers to events that result in a substantial disruption of a subject’s ability to conduct normal life function.
- Is a congenital anomaly or birth defect;
- Is an important medical event (IME):

- Note: The term “important medical event” refers to an event that, based upon appropriate medical judgment, may not be immediately life-threatening or result in death or hospitalization, but may jeopardize the subject or require intervention to prevent one of the other serious outcomes listed. Examples of IMEs include intensive treatment in an emergency room or at home for allergic bronchospasm; blood dyscrasias, or convulsions that do not result in hospitalization; or development of product dependency or product abuse.

6.1.3 Relationship to Study Treatment

Assessment of the relationship of the AE to the study treatment by the investigator is based on the following two definitions:

- Not Related: A not-related AE is defined as an AE that is not associated with the study treatment and is attributable to another cause or there is no evidence to support a causal relationship;
- Related: A related AE is defined as an AE where a causal relationship between the event and the study treatment is a reasonable possibility. A reasonable causal relationship is meant to convey that there are facts (e.g., evidence such as dechallenge/rechallenge) or other clinical arguments to suggest a causal relationship between the AE and study treatment. Possibly and probably related AEs should be documented as related.

6.1.4 Serious Adverse Event Reporting

As soon as an investigator becomes aware of an AE that meets the definition of ‘serious,’ this must be documented on an SAE Report Form or in an electronic database and include the following: (i) all SAEs that occur after starting cabozantinib and through 30 days after the decision to discontinue study treatment and (ii) any SAEs assessed as related to study treatment or study procedures, from the time of first study drug dose, even if the SAE occurs more than 30 days after the decision to discontinue study treatment.

All SAEs that are assessed by the PI as related to drug or study procedure and all pregnancy/lactation reports regardless of outcome must be sent to Exelixis within one (1) business day of the PI’s knowledge of the event. The reports must be sent to [contact] or [contact].

- The PI will perform adequate due diligence with regard to obtaining follow-up information on incomplete reports. All follow-up information must be sent to Exelixis within one (1) business day of the PI’s receipt of the new information. Upon Exelixis request, the PI will query for follow-up information.

6.1.5 Regulatory Reporting

The Investigator will assess the expectedness of each related SAE. The current cabozantinib Reference Safety Information (Appendix K of the most recent approved Investigator Brochure) will be used as the reference document for assessing the expectedness of the event with regard to cabozantinib. All serious unexpected adverse drug reactions (unexpected related SAEs) must be reported to all appropriate regulatory authorities and Ethics Committees by the investigator as required by 21 CFR 312.32 or by Directive 2011/20/EC:

- These reports are to be filed utilizing the Form FDA 3500A (MedWatch Form) or a CIOMS-1 form;
- Exelixis reserves the right to upgrade the Investigator assessment of an SAE based on Exelixis assessment.
- Institutions and PIs shall promptly provide all information requested by Exelixis regarding all adverse events occurring during the conduct of the study.
- The PI is responsible for complying with all regulatory authority reporting requirements for the study that are applicable to the sponsor of a clinical trial. The PI shall provide a

copy of all responses to regulatory agency requests, periodic reports, and final study reports to Exelixis within one (1) business day of the submission.

- Exelixis will provide relevant product safety updates and notifications, as necessary. In the case of multi-center studies, it is the responsibility of the sponsoring PI/Institution to disseminate these updates to participating PIs.

6.2 Other Safety Considerations

6.2.1 Laboratory Data

All laboratory data required by this protocol and any other clinical investigations should be reviewed. Any abnormal value that leads to a change in subject management (eg, dose reduction or delay or requirement for additional medication or monitoring) or that is of clinical significance by the investigator should be reported as an AE or SAE as appropriate.

6.2.2 Pregnancy/Lactation Exposure

If a subject becomes pregnant during the study, she will be taken off study treatment and will be followed through the end of her pregnancy. Pregnancy (in subject or partner) or lactation exposure, although not an SAE, should be reported to Exelixis. Forms will be provided to the study sites upon request. The outcome of a pregnancy (for a subject or for the partner of a subject) and the medical condition of any resultant offspring must be reported to Exelixis. Any birth defect or congenital anomaly must be reported as an SAE, and any other untoward events occurring during the pregnancy must be reported as AEs or SAEs, as appropriate.

6.2.3 Medication Errors/Overdose

Any overdose, or study drug administration error that results in an AE, even if it does not meet the definition of serious, requires reporting within one (1) business day to Exelixis.

6.2.4 Follow-Up of Adverse Events

Any related SAEs or any AEs assessed as related that led to treatment discontinuation, including clinically significant abnormal laboratory values that meet these criteria, ongoing 30 days after the decision to discontinue study treatment must be followed until either resolution of the event or determination by the investigator that the event has become stable or irreversible. This follow-up guidance also applies to related SAEs that occur more than 30 days after the decision to discontinue study treatment. The status of all other continuing AEs will be documented as of 30 days after the decision to discontinue study treatment.

7 STATISTICAL CONSIDERATIONS

7.1 Analysis Population

7.1.1 Safety Population

The safety population will consist of all subjects who receive any amount of study treatment.

7.2 Safety Analysis

Safety will be assessed by evaluation of AEs. All safety analyses will be performed using the safety population.

7.2.1 Adverse Events

Adverse event terms recorded on the CRFs will be mapped to preferred terms using the Medical Dictionary for Regulatory Activities (MedDRA). Seriousness, severity grade and relationship to study treatment will be assessed by the investigator. Severity grade will be defined by the National Cancer Institute (NCI) CTCAE v4.0. Listings of AEs will be provided.

7.3 Sample Size

The stage I sample size will consist of 16 subjects for interim analysis, then an additional 28 subjects for stage II for a total of 44 subjects.

7.3.1 Sample Size Justification

Based on the phase III CORRECT trial investigating regorafenib versus best supportive care, the median PFS for patients with refractory colorectal cancer was 1.7 months in the placebo arm. Therefore, the PFS at 12 weeks would be approximately 13%, which will serve as the response rate in the null hypothesis. We have designed the trial to have at least 90% power to detect an improvement in the 12-week PFS rate of at least 20%, therefore the alternative hypothesis is that the 12-week PFS rate is 33%. The optimal design providing at least 90% power to detect the alternative while controlling the type I error rate at 0.05 uses at most 44 patients. This design has an actual type I error rate of 0.0441 (i.e. if the true 12-week PFS rate is less than or equal to 0.13, there is only a 4.4% probability of concluding that the PFS rate is greater than or equal to 0.33). This design has power of 0.906 to detect the alternative hypothesized 12-week PFS rate of 0.33. This trial design uses an average of 25.7 patients.

8 OTHER ANALYSES

8.1 Analytic Plan Primary, Secondary, and Exploratory Endpoints

8.1.1 Primary Endpoint:

Progression-free survival will be defined as the time from administration of the initial dose of cabozantinib to evidence of radiographic progression as defined by RECIST criteria or death from any cause without evidence of disease progression, whichever occurs first. Each patient will be examined for PFS at 12 weeks and dichotomized as either having progression or not. Using an optimal Simon 2-stage design, the first 16 patients will be enrolled and 12-week PFS will be determined. If 3 or more of these patients have not progressed by 12 weeks, the trial will accrue an additional 28 patients for a total of 44 patients. If 10 or more (total) of these 44 patients are free of progression at 12 weeks then the Null Hypothesis will be rejected in favor of the alternative suggesting that the treatment has sufficient efficacy to warrant future study.

Kaplan-Meier estimates of PFS rates will be calculated along with their corresponding 95% confidence intervals.

Evaluable for Response

Only those participants who have received at least 2 cycles of therapy, and have had their disease re-evaluated will be considered evaluable for response. Note: Participants who exhibit objective disease progression or die prior to Cycle 3 will also be considered evaluable. Participants who do not meet the criteria for being evaluable for response defined above may be replaced to reach the sample size necessary for interim analysis.

8.1.2 Secondary Endpoints:

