- 1) To determine the clinical activity of cabozantinib in patients with refractory metastatic CRC using progression free survival (PFS) as primary endpoint.

Secondary Objectives:

- 1) To determine the response rate (RR) in patients with refractory metastatic CRC treated with cabozantinib.
- 2) To determine the overall survival (OS) in patients with refractory metastatic CRC treated with cabozantinib.
- 3) To describe safety and tolerability of cabozantinib in this group of heavily pretreated patients.
- 4) To retrospectively explore the PFS and RR in patients based on RAS, BRAF, and PIK3CA mutation status.

Exploratory Objectives:

- 1) Exploratory analysis of predictive and pharmacodynamic markers.

[figure not shown]
STUDY DESIGN

This is an open-label, single-arm, 2-stage Phase II study of cabozantinib, a small molecule inhibitor of multiple receptor tyrosine kinases (RTKs) including MET, VEGFR2, RET, AXL, and KIT, in patients with refractory metastatic CRC. Up to 44 evaluable patients will be treated with cabozantinib at a dose of 60 mg daily. One cycle is defined as 21 days.

The primary endpoint is 12-week progression-free survival (PFS). The study will undergo one interim monitoring for futility when 16 evaluable patients have been accrued and dosed, and at least 3 patients have met the 12 week PFS time point. If 2 or fewer patients have a PFS of ≥ 12 weeks, then the study will be terminated. If 3 or more patients have a PFS of ≥ 12 weeks, an additional 28 patients will be enrolled for a total accrual of 44 patients.

Assessment of tumor response will be performed every 6 weeks for the first 12 weeks on study. After 12 weeks, assessment of response will be every 9 weeks. The modified Response Evaluation Criteria in Solid Tumors (RECISTv1.1) will be used to establish disease response or progression.

All patients will be evaluated and graded for adverse events according to the NCI Common Terminology for Adverse Events, version 4.0 (CTCAE).

NUMBER OF SUBJECTS

Approximately 44 subjects will be eligible for this study.

(16 patients in stage 1 + 28 patients in stage 2 = 44 total patients)

TARGET POPULATION

Colorectal cancer patients will be eligible for enrollment as defined by the inclusion and exclusion criteria as follows:

Inclusion criteria - A subject must fully meet all the following criteria to be eligible for the study:

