 - a) Exploratory analysis of predictive and pharmacodynamic markers by obtaining pre- and post-treatment whole blood samples pretreatment and +/- 5 days of Cycle 3 Day 1 of treatment for each patient and archived for future studies and analysis.
4. Analytic plan for primary objective:
 - a) PFS – each patient will be examined for PFS at 12 weeks and dichotomized as either having progression or not. Using an optimal Simon 2-stage design the first 16 patients will be enrolled and 12-week PFS will be determined. Study enrollment will continue after the 16th patient is accrued and dosed, and at least 3 patients have met the 12 week PFS time point. If 3 or more of these patients have not progressed by 12 weeks, the trial will accrue an additional 28 patients for a total of 44 patients. If 10 or more (total) of these 44 patients are free of progression at 12 weeks, then the Null Hypothesis will be rejected in favor of the alternative suggesting that the treatment has sufficient efficacy to warrant future study.
 - i. PFS – Kaplan-Meier estimates of progression-free survival rates will also be calculated along with their corresponding 95% confidence intervals.
5. Analytic plan for secondary objectives:
 - a) RR - defined using the RECIST criteria as the proportion of subjects with a confirmed CR or confirmed PR. The point estimate of the RR with a 95% confidence interval based on the exact binomial distribution will be presented.
 - b) OS – Kaplan-Meier estimates of progression-free survival rates will be calculated along with their corresponding 95% confidence intervals.
 - c) Safety and tolerability analysis - all enrolled patients who receive at least one dose of cabozantinib will have information collected on adverse events, which will be summarized by dose and severity as assessed by the Common Toxicity Criteria for Adverse Events (CTCAE) v. 4.0 and relationship to Study Drug.
 - d) Retrospective analysis of the PFS and RR in patients based on RAS, BRAF, and PIK3CA mutation status - point estimates with 95% confidence intervals will be provided for each group, and comparisons will be made using a stratified log-rank test.

6. Analytic plan for exploratory analysis:
 - a) Exploratory analysis – peripheral blood collections pretreatment and +/- 5 days of Cycle 3 Day 1 will be obtained and archived for future investigation of predictive and pharmacodynamics biomarkers.
7. Sample size justification:

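### The cut-offs of 3 of 16 and 10 of 44 are fixed, but the patients who fill those counts are not: early stoppers without documented progression may be replaced

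*Combined protocol and SAP*

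**What the plan says.** The trial-level rule is the same wherever it appears: 16 patients, then 28 more; continue if 3 or more are progression-free at 12 weeks; reject the null hypothesis at 10 or more of 44 (Synopsis, Statistical Methods, item 4a; Sections 7.3 and 8.1.1).

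Who is counted is described in several ways:

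- Synopsis, Study Design: "Up to 44 evaluable patients will be treated with cabozantinib", with the interim look "when 16 evaluable patients have been accrued and dosed".
- Section 7.3: 16 subjects, "then an additional 28 subjects for stage II for a total of 44 subjects", without the word evaluable.
- Section 8.1.1, under the primary endpoint: "Only those participants who have received at least 2 cycles of therapy, and have had their disease re-evaluated will be considered evaluable for response". An exception keeps early events: "Participants who exhibit objective disease progression or die prior to Cycle 3 will also be considered evaluable". Of the remaining patients, the section says that they "do not meet the criteria for being evaluable for response defined above may be replaced to reach the sample size necessary for interim analysis".
- Section 7.1.1 defines a safety population of everyone who received any study treatment. No efficacy population is defined.
- Section 3.4.4 says that patients given palliative bone radiation may be treated as not evaluable, or given a censoring or a progression date, for some efficacy endpoints. It does not say which.

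Success for a patient also has two wordings. The futility rule in the Synopsis, Study Design, reads: "If 2 or fewer patients have a PFS of ≥ 12 weeks, then the study will be terminated". Item 4a and Section 8.1.1 ask whether the patient is without progression by week 12, and the final rule reads: "If 10 or more (total) of these 44 patients are free of progression at 12 weeks". Table 5-1 allows ±5 days around visits, and the text after it lets a missed assessment be done as near to schedule as possible.

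**The concern.** The trial has no control arm. Its conclusion is a count compared with a fixed 13%, so a patient removed from the count is as important as one added to it, and one patient can decide either cut-off.

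The replaceable group is not a random sample. Section 5.5.1.4 describes patients who stop for general decline without objective progression at that time. Section 2.6 allows stopping for adverse events or loss of clinical benefit. Unless progression or death is recorded before Cycle 3, such a patient may be replaced, although many would not have been progression-free at week 12. If so, the counted rate is too high and an inactive drug passes more often than planned.

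The two success wordings differ for progression found on a scan at exactly day 84. PFS is then 12 weeks, which satisfies the futility wording, but the patient is not free of progression at week 12.

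**Working it through.** **Inputs.** Null rate 0.13, alternative 0.33, type I error 0.0441, power 0.906 and average sample size 25.7 (Section 7.3.1); cut-offs 3 of 16 and 10 of 44 (Section 8.1.1). The documents give neither the share of patients excluded (d) nor those patients' success rate (q), so both are assumed.

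**Step 1: reproduce the plan.** With success rates p1 in stage 1 and p2 in stage 2:

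P(reject) = sum over x = 3 to 16 of P(X1 = x | 16, p1) × P(X2 ≥ 10 − x | 28, p2)

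- p1 = p2 = 0.13: 0.0441.
- p1 = p2 = 0.33: 0.9055.
- Chance of passing the interim at 0.13: 0.346.
- Average sample size at 0.13: 16 + 28 × 0.346 = 25.7.

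The plan's figures are right, provided every counted patient has the stated success rate.

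**Step 2: replacement.** If 13% is the all-dosed rate, the rate among counted patients is

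p = (0.13 − q × d) / (1 − d)

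For d = 0.05 and q = 0: 0.13 / 0.95 = 0.1368. For d = 0.10 and q = 0: 0.13 / 0.90 = 0.1444. In the stage 1 only column, stage 2 stays at 0.13.

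| q | d | p | Pass interim | Type I error, stage 1 only | Type I error, both stages |
|---|---|---|---|---|---|
| 0 (all would fail) | 5% | 0.1368 | 0.378 | 0.050 | 0.059 |
| 0 | 10% | 0.1444 | 0.413 | 0.058 | 0.079 |
| 0.065 (half the null rate) | 5% | 0.1334 | 0.362 | 0.047 | 0.051 |
| 0.065 | 10% | 0.1372 | 0.380 | 0.051 | 0.060 |
| 0.13 (unrelated to outcome) | any | 0.1300 | 0.346 | 0.0441 | 0.0441 |
| 0.20 (better than null) | 5% | 0.1263 | 0.329 | 0.041 | 0.037 |
| 0.20 | 10% | 0.1222 | 0.310 | 0.038 | 0.031 |

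With q = 0, type I error passes 0.05 at about 4.8% excluded (stage 1 only) or 2.2% (both stages).

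**Step 3: the looser futility wording.** Let f be the share of week-12-scan progressions credited as successes at the interim only. Assume 25% are progression-free at week 6. The interim rate is 0.13 + f × (0.25 − 0.13), and the final count keeps the stricter wording.

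| f | Interim rate | Pass interim | Type I error |
|---|---|---|---|
| 1% | 0.1312 | 0.352 | 0.0442 |
| 2% | 0.1324 | 0.357 | 0.0443 |
| 5% | 0.1360 | 0.374 | 0.0447 |
| 10% | 0.1420 | 0.402 | 0.0453 |

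The 25% may be low. The 1.7-month placebo median is about 7.4 weeks (1.7 × 30.4 / 7), which puts at least half of patients progression-free at week 6. With 50% and f = 10%, the interim rate is 0.13 + 0.10 × 0.37 = 0.167 and the pass probability is 0.515. The ceiling on type I error does not depend on this assumption: even if every trial passed the interim, P(X ≥ 10 | 44, 0.13) = 0.0527.

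**The case against.** Much of the other side's case stands. The counts and cut-offs are consistent and reproduce 0.0441, so a reader who infers that the trial has no denominator or no decision rule goes further than the documents allow. Patients who progress or die before Cycle 3 stay in, which removes the most obvious bias. Section 5.5.1.4 asks for progression to be documented after stopping, and Section 5.3 follows disease status, so the affected group may be small. Replacement is optional and worded for the interim; extending it to all 44 rests on one phrase in the Synopsis. Kaplan-Meier PFS rates are also planned and can include incompletely followed patients, although they do not drive the decision. The null is itself only approximate: at a true rate of 14% the rejection probability is already 0.067.

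Two stronger readings are tempting. One is that the true type I error exceeds 0.05. The documents cannot show that, because they give no exclusion rate, no outcome for excluded patients, and no statement of whether 13% means dosed or evaluable patients. The other is that the two success wordings inflate the final test. The looser wording appears only in the futility rule. Values of 0.0465 to 0.0721 (f = 1% to 10%, 25% progression-free at week 6) would need a loose reading, or a lenient late-scan rule, at both stages.

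What is not answered is how a patient who stops early without documented progression, or who has no usable week-12 scan, enters the count.

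**Conclusion.** The concern holds as a gap in patient-level classification. The stated 0.0441 is exact if the counted patients have the 13% rate, which requires either that 13% was meant for evaluable patients or that exclusion is unrelated to outcome. If 13% is the all-dosed rate and excluded patients would all fail, 5% to 10% excluded moves type I error to 0.050–0.058 on the literal interim-only reading, or 0.059–0.079 if replacement extends to both stages. An inactive drug's chance of passing futility rises from 0.346 to 0.378–0.413. These are assumed shares, and the direction reverses if excluded patients do better than the null rate.

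The difference in wording is the smaller matter. It weakens the futility stop and barely affects type I error, which cannot exceed 0.0527 by that route. The plan should be changed, because two analysts following it could reach different counts from the same data. How confident one can be about the size is limited by the missing inputs.

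**What to change.** - Base the primary decision on the first 16 and first 44 dosed patients, using the population in Section 7.1.1, without replacement. Count a patient with no assessable week-12 status as a failure.
- Use one definition of success in the Synopsis (Study Design and item 4a) and Section 8.1.1: alive, with no RECIST progression up to and including the week-12 scan (±5 days).
- State a rule for late scans. For example, a later scan without progression is a success; progression on a late scan, with no progression-free scan inside the window, is a failure.
- Reconcile Section 3.4.4 with this definition, so that the classification of irradiated patients is settled in advance.
- Keep the evaluable set as a sensitivity analysis, and report the number of non-evaluable patients with reasons.
- Have the sponsor state whether 13% and 33% describe dosed or evaluable patients.

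The cost is a text amendment, with the company and IRB approvals that Section 13 requires, best made before week-12 results are reviewed. The reported rate will be slightly lower. If the rates were meant for all dosed patients, power and type I error are unchanged. If they were meant for evaluable patients, the all-dosed rate is p × (1 − d). At 5% or 10% non-evaluable, 0.33 becomes 0.3135 or 0.297, with power 0.870 or 0.823, and type I error is 0.0326 or 0.0235. That power should be restated rather than met by enrolling more patients.
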